8.1.5 Pregnancy

Pregnancy itself is not regarded as an AE unless there is a suspicion that the IMP has interfered with a contraceptive method. If pregnancy occurs during the study, the outcome of the pregnancy will then need to be collected poststudy and it may be necessary to discontinue administration of the IMP.

Information regarding pregnancies must be collected on the AE page of the eCRF and reported to the sponsor within 24 hours. The sponsor will request further information from the investigator as to the course and outcome of the pregnancy using the Standard Pregnancy Outcome Report Form.

The investigator must instruct all female subjects to inform them immediately should they become pregnant during the study. The investigator should counsel the subject, discuss the risks of continuing with the pregnancy and the possible effects on the foetus. Monitoring of the subject should continue until conclusion of the pregnancy, which may involve follow up after the subject's involvement in the study has ended.

Pregnancies with a conception date within 180 days after subject's last dose of IMP must be reported to the investigator for onward reporting to the sponsor.

8.1.6 **Deaths**

All AEs resulting in death during the study period must be reported as an SAE within 24 hours of the investigator's knowledge of the event.

The convention for recording death is as follows:

- AE term: lead cause of death (e.g. multiple organ failure, pneumonia, myocardial infarction)
- outcome: fatal.

The **only exception** is if the cause of death is unknown (i.e. sudden or unexplained death), in which case the AE term may be "death" or "sudden death".

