- at Week 12: the investigator will decide if the subject is still responding to treatment or if a further injection is needed, based on his/her clinical judgement. If a further injection is needed, the subject completes the study after study assessments have been performed (before the injection outside the study is given) (i.e. Final Visit). If a further injection is not needed, the subject will return at Week 16;
- at Week 16: the investigator will again decide if the subject is still responding to treatment or if a further injection is needed, based on his/her clinical judgement. If a further injection is needed, the subject completes the study after study assessments have been performed (before the injection outside the study is given) (i.e. Final Visit). If a further injection is not needed, the subject will return at Week 20;
- at Week 20: the subject completes the study after study assessments have been performed, regardless of whether a further injection is needed (i.e. Final Visit).

[figure not shown]
The overall duration of the study for each subject will be between 24 and 40 weeks (from Baseline Visit to Final Visit).

Subjects who receive two AbobotulinumtoxinA administrations and complete the required postinjection FU visits will be considered to have completed the study.

Subjects who withdraw from the study before completion of scheduled visits will have Early Withdrawal Visit assessments performed at their last visit.

PROTOCOL FINAL (INCLUDING AMENDMENT #2): 24 JANUARY 2018

PAGE 29/105

PROTOCOL FINAL (INCLUDING AMENDMENT #2): 24 JANUARY 2018

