3.5 Study Duration

This study will consist of two open-label injection (treatment) cycles. Each cycle will include postinjection FU visits of up to 20 weeks (see Section 3.1). Subjects are expected to participate in this study for a minimum of 24 weeks (if they have postinjection FU visits up to Week 12 only, following both injections) and a maximum of 40 weeks (if they have postinjection FU visits up to Week 20, following both injections).

The subject's participation in the study will be considered to have ended at the time of the Final Visit. This will be no later than 20 weeks after the second AbobotulinumtoxinA injection.

The overall duration of the study will be between approximately 15 and 18 months. The study will be considered to have started when the first subject provides signed informed consent.

The study will be considered to have ended after the last subject has completed his/her Final Visit.

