- e For all subjects attending the Week 20 visit (Cycle 2), this will be the Final Visit.
- f Informed consent must be obtained before the subject undergoes any study-specific procedures.
- g Demographics: sex and date of birth; race and ethnicity will also be collected if permitted according to local regulations.
- h Disease history: date and type of ABI, date of spasticity development.

PAGE 39/105

PROTOCOL FINAL (INCLUDING AMENDMENT #2): 24 JANUARY 2018

F-FR-52120-228

- i Record all details of previous GSC or physiotherapy within 4 months before Baseline..
- j Record if subject is naïve or non-naïve to BoNT treatment; if non-naïve to BoNT treatment, record dates of the first injection and last injection, which limbs were injected, and BoNT brand and dose used in the last injection.
- k Medical history: any significant past or ongoing medical or surgical conditions (not related to UL or LL spasticity).
- Prior and concomitant medications for UL or LL spasticity: therapies taken from 4 weeks prior to baseline through the study (including the subject's last study visit).
- m Prior and concomitant medications and nondrug therapies: therapies taken from 4 weeks prior to baseline through the study (including the subject's last study visit).
- n Urine pregnancy test: recorded for females of childbearing potential only.
- o Measured at Baseline Visit, second injection visit and Final Visit, only (or early withdrawal). Vital signs: diastolic and systolic blood pressure and heart rate measured in the supine position after 5 minutes rest. Weight will be measured at baseline, second injection and last visit; height will be measured at baseline only.
- p To be performed at the Final Visit (which may be Week 12, Week 16 or Week 20 after Injection 2) or early withdrawal.
- q AROM is measured in each muscle group of the UL and LL (irrespective of whether injected or not).
- r WST is to be performed in the same condition as at Baseline Visit, for example, if a cane was used at the Baseline Visit, the same cane should be used for this test at other visits.
- s The number of days when GSC therapy was not performed since the last visit, as recorded in the subject diary, will be counted and recorded in the eCRF.
- t To be performed only at the last postinjection FU visit after Injection 1 (i.e. the visit where second injection is performed, which may be Week 12, Week 16 or Week 20).

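### The instruction to women in Section 8.1.5 to notify pregnancies covers a shorter period than the 180-day reporting window in the same section

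*Protocol*

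**What the plan says.** Two rules stand close together in protocol Section 8.1.5. The first concerns what women are told: "The investigator must instruct all female subjects to inform them immediately should they become pregnant during the study". The second sets the reporting window: "Pregnancies with a conception date within 180 days after subject's last dose of IMP must be reported to the investigator for onward reporting to the" (the onward recipient is the sponsor). The second rule does not say who makes the report to the investigator, and it does not require anyone to tell subjects about the 180 days.

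Section 3.5 gives two end points. For the individual: "The subject's participation in the study will be considered to have ended at the time of the Final Visit", and "This will be no later than 20 weeks after the second AbobotulinumtoxinA injection". For the trial as a whole: "The study will be considered to have ended after the last subject has completed his/her Final Visit". Footnote p to Table 2 in Section 5.1 fixes when the Final Visit can fall, in describing the assessments tied to it: "To be performed at the Final Visit (which may be Week 12, Week 16 or Week 20 after Injection 2) or early withdrawal".

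**The concern.** A report to the investigator after the Final Visit depends on someone passing on the information, and the subject is the obvious source. The only explicit instruction to her is limited to the study period, whereas the reporting rule runs to 180 days after the last dose.

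Nothing else in the protocol body closes the difference:

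- Table 2 schedules the urine pregnancy test at baseline only.
- The two-weekly telephone calls support the rehabilitation contract, which Section 6.1 runs to the Final Visit. No later contact is scheduled.
- The procedures listed in Section 5.2.2 for visits that may be the Final Visit, and in Section 5.2.3 for early withdrawal, include no reminder about notifying a pregnancy.
- Section 8.1.4 asks for prompt reporting of suspected related adverse events after completion, but Section 8.1.5 does not count a pregnancy as an adverse event unless interference with contraception is suspected.
- The follow-up beyond a subject's involvement that Section 8.1.5 foresees is for pregnancies already known to the site.

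At stake is the completeness of pregnancy data in part of the window that the sponsor itself has set.

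**Working it through.** **Inputs.** Reporting window: 180 days after the last dose (Section 8.1.5). Final Visit: Week 12, 16 or 20 after the second injection (Section 5.1, Table 2, footnote p). Visit windows: +7 days at Week 12, ±7 days at Weeks 16 and 20 (Table 2).

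**The plan's own figure.** The shortest course is 12 + 12 = 24 weeks and the longest 20 + 20 = 40 weeks. This matches the 24 to 40 weeks per subject in Sections 3.1 and 3.5, so the visit schedule is being read as the plan intends.

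**Reading 1: the instruction covers the subject's own participation.** Uncovered days = 180 − (weeks to Final Visit × 7).

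| Final Visit after injection 2 | Nominal day | Uncovered days | Share of 180 | Days allowed by visit window | Uncovered days over that window |
|---|---|---|---|---|---|
| Week 12 | 84 | 180 − 84 = 96 | 53% | 84 to 91 | 89 to 96 |
| Week 16 | 112 | 180 − 112 = 68 | 38% | 105 to 119 | 61 to 75 |
| Week 20 | 140 | 180 − 140 = 40 | 22% | 133 to 147 | 33 to 47 |

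Even at the latest day that the visit window allows (147), 33 days remain, so on this reading every completer has a gap. For a subject who leaves d days after her last injection, the gap is 180 − d. Leaving at the nominal Week 6 visit, for example, gives 180 − 42 = 138 days (77%), and leaving sooner gives more.

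**Reading 2: the instruction covers the whole study.** Let L be the number of days from a subject's last dose to the last subject's Final Visit. Uncovered days = 180 − L if L is below 180, and 0 otherwise. Anyone last dosed 180 days or more before the study closes is fully covered. For the subject who finishes last, L is 84, 112 or 140, so her gap is again 96, 68 or 40 days. Coverage then depends on when a woman happened to enrol. The documents do not give the enrolment dates needed to say how many women this leaves.

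**The case against.** The best reply is that the two sentences add to each other. The first asks for immediate notice while decisions about further study drug and counselling may be pending. The second sets a longer window, and a site that complies with the whole section must arrange to hear of conceptions up to day 180. It is also fair that Section 8.1.5 never says women need notify at no other time, and that Section 4.3 has the investigator arrange follow-up for withdrawn subjects where required.

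Part of this stands. A reader might infer that the two rules contradict each other. They do not: both can be obeyed at once, and they differ in coverage. What the reply does not supply is the missing link. The 180-day sentence names no reporter and creates no duty to tell subjects, so the additive reading leaves each site to work out for itself how the report should arise.

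A reader might also infer that sites will not learn of later pregnancies and that the sponsor cannot meet its own rule. The documents do not support that. A woman may volunteer the information. She may also have been told of the 180 days in the consent form, whose pages were not available for review, or on the emergency contact card mentioned in Section 1.5.

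Finally, the day counts for completers in general depend on taking the instruction to mean individual participation. Section 3.5 also defines the end of the study as a whole, and Section 8.1.5 uses a different expression when it means the individual subject's involvement. The study-level reading is therefore open. It narrows the gap but does not remove it.

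**Conclusion.** The point holds as a mismatch of coverage within Section 8.1.5. Read per subject, completers have 96, 68 or 40 of the 180 days outside the explicit instruction, and subjects who withdraw soon after an injection have more. Read at study level, only those whose 180 days extend past the last subject's Final Visit are affected.

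On either reading, sites that follow the instruction as written may not learn of some reportable pregnancies, and the protocol body states no means of meeting the reporting rule for them. How many women this concerns cannot be derived, because the documents give no number of women of childbearing potential; it may be small. The primary endpoint, analysis populations, sample size and efficacy analyses are untouched. This is a worthwhile minor correction to safety reporting.

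**What to change.** Reconcile the two sentences in Section 8.1.5 so that the instruction to notify covers the same 180 days after the last dose that the section already sets for reporting. Add a reminder of this to the procedures for the Final Visit and the Early Withdrawal Visit (Sections 5.2.2 and 5.2.3), and check that the consent form and other subject-facing documents state the same period. If the consent form already does, the protocol only has to be brought into line with it.

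The cost is one sentence in Section 8.1.5 and a reminder at a visit that takes place anyway. No extra visit, test or staff is needed, and no change to contraception, testing or dosing rules is proposed.

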8.1.7 Discontinuation/Withdrawal due to Adverse Events/Serious Adverse Events

Discontinuation/withdrawal due to AEs should be distinguished from discontinuation/withdrawal due to other reasons (see Section 4.3).

If the IMP is discontinued due to a SAE, it must be reported immediately to the sponsor's designated representative (see Section 8.1.4).

In all cases, the investigator must ensure the subject receives appropriate medical follow up (see Section 8.1.3).

8.1.8 Reporting to Competent Authorities/IECs/IRBs/Other Investigators

The sponsor will ensure that processes are in place for submission of reports of Suspected Unexpected Serious Adverse Reactions (SUSARs) occurring during the study to the CAs, IECs and other investigators concerned by the IMP. Reporting will be done in accordance with the applicable regulatory requirements.

For study centres in the USA, Investigational New Drug application Safety Reports will be submitted directly to the investigators. It is the investigators' responsibility to notify their IRB in a timely manner.

8.2 Physical Examination

Physical examinations will be performed by a physician at the visits indicated in Table 2.

PROTOCOL FINAL (INCLUDING AMENDMENT #2): 24 JANUARY 2018

Any clinically significant physical examination findings (abnormalities) observed during the study will be reported as AEs.

A urine pregnancy test will be performed at the Baseline Visit for all female subjects of childbearing potential.

8.3 Vital Signs

Blood pressure and heart rate will be recorded after 5 minutes of rest in a supine position at the visits indicated in Table 2.

Body weight will be measured at the visits indicated in Table 2. Height will be measured at the Baseline Visit only.

See Section 8.1.2.6 for abnormal vital signs results that should be recorded as AEs in the eCRF.

PROTOCOL FINAL (INCLUDING AMENDMENT #2): 24 JANUARY 2018

PAGE 64/105

9 ASSESSMENTS OF PHARMACOKINETICS/PHARMACODYNAMICS

Pharmacokinetics and pharmacodynamics are not assessed in this study.

PROTOCOL FINAL (INCLUDING AMENDMENT #2): 24 JANUARY 2018

10 STATISTICS

10.1 Analyses Populations

The following populations will be used during the statistical analyses:

- Screened population: all subjects screened (i.e. who signed the informed consent).
- Safety population: all subjects who received at least one dose of study medication.
- **Intent-to-treat (ITT) population:** all subjects who received at least one dose of study medication. The ITT population will be identical to the safety population and will be denoted throughout as safety/ITT population.
- **Modified intent-to-treat (mITT) population:** all treated subjects having the primary efficacy outcome assessed at Week 6 after the second injection.
- **Per protocol (PP) population:** all subjects in the mITT population for whom no major protocol violations/deviations occurred.

10.1.1 Populations Analysed

The primary analysis based on the primary efficacy endpoint will be performed on the mITT population. In addition, safety/ITT and PP analyses will be performed as secondary analyses.

10.1.2 Subject Allocation and Reasons for Exclusion from the Analyses

Any major protocol deviation will be described in the Protocol Deviation Document and its impact on inclusion in each analysis population (mITT, safety/ITT and PP populations) for any subject will be specified. The final list of protocol deviations impacting all populations will be reviewed during the final data review meeting held prior to database lock.

10.2 Sample Size Determination

The sample size was determined based on the primary efficacy endpoint (percentage of responder subjects at Week 6 after the second injection according to composite AROM). A 60% response rate was assumed based on previous studies (adult UL/LL) with an additional benefit of $\pm 10\%$ compared with that observed in these studies (approximately 50% response rate at Week 4 of Cycle 2). The aim of this study will be to estimate this proportion with an accuracy of $\pm 8\%$. Given a two-sided 95% confidence interval (CI), 145 subjects are required; with an assumed 5% dropout rate, 153 subjects will have to be enrolled to achieve a target of 145 evaluable subjects (i.e. subjects included in the mITT population). These calculations have been performed with nQuery using CI for proportions and assuming normal approximation.

10.3 Significance Testing and Estimations

As this is a descriptive efficacy study, no formal statistical testing will be performed and all the analyses will be primarily descriptive in nature. When appropriate and unless otherwise specified, two-sided 95% CIs will be displayed and if p-values are presented, they will be for exploratory purposes only.

Descriptive statistics will include number of measures (n), n missing and the following:

- mean, standard deviation, minimum, median, maximum and 95% CIs for means for interval-type variables
- counts and percentages of each category for categorical nominal variables
- both the above for categorical ordinal variables.

PROTOCOL FINAL (INCLUDING AMENDMENT #2): 24 JANUARY 2018

10.4 Statistical/Analytical Methods

The statistical analyses will be performed by an external CRO, managed by the sponsor's Biometry Department.

A statistical analysis plan (SAP) describing the planned statistical analysis in detail with tables, figures and listings templates will be developed as a separate document.

Statistical evaluation will be performed using Statistical Analysis System (SAS)[®] (Version 9 or higher).

10.4.1 Demographic and Other Baseline Characteristics

All demographic and baseline characteristics will be listed for the safety/ITT population.

Descriptive summary statistics for demographic and baseline characteristics will be presented for the mITT population. If the safety/ITT population differs from the mITT population by more than 10%, summary statistics for demographic and baseline characteristics will also be presented for the safety/ITT population.

10.4.2 Homogeneity of Treatment Groups

Not applicable as this is a single treatment arm study.

10.4.3 Subject Disposition and Withdrawals

The numbers and percentages of subjects enrolled and included in each of the mITT, safety/ITT and PP populations will be tabulated by country and centre. The reasons for subject exclusions from each of the populations will also be tabulated. In addition, the numbers of subjects who were treated, discontinued and completed the study treatment will be tabulated for each population. Primary reasons for discontinuation of study treatment will be tabulated.

10.4.4 Pharmacokinetic Data

There are no PK analyses planned for this study.

10.4.5 Efficacy Evaluation

10.4.5.1 Primary Efficacy Endpoint

As indicated in Section 7.1, the primary efficacy endpoint is as follows:

• the percentage of responder subjects at Week 6 after the second injection, according to composite AROM in the primary TT limb.

Composite AROM (X_A), regardless of whether the muscle groups were injected or not, as measured by goniometer in the primary TT limb (either UL or LL, depending on which one has been selected as the primary TT limb), will be calculated as follows:

- composite X_A UL: X_A UL = X_{AEF} + X_{AWF} + X_{AFF}
- composite $X_A LL$: $X_A LL = X_{Asol} + X_{AGN}$

where for UL: EF=elbow flexors, WF=wrist flexors and FF=extrinsic finger flexors, and for LL: Sol=soleus and GN=gastrocnemius muscles.

Definition of a responder: a subject will be considered a responder if he/she achieves at least the predefined improvement threshold - larger or equal to 35° in UL or 5° in LL - in the primary TT limb (based on the composite AROM individual change from baseline to Week 6 after the second injection).

PROTOCOL FINAL (INCLUDING AMENDMENT #2): 24 JANUARY 2018

Primary Efficacy Analysis of the Primary Efficacy Endpoint

The primary efficacy endpoint will be summarized descriptively as a binary variable using the mITT population.

Secondary Efficacy Analysis of the Primary Efficacy Endpoint

The following analyses will be conducted in support of the primary efficacy analysis.

The primary efficacy analysis will be repeated using the safety/ITT population where subjects with missing responder status at Week 6 after the second injection will have their last postbaseline responder status used instead. Subjects with no postbaseline responder status are considered nonresponders.

Additionally, the primary efficacy analysis will be repeated based on the PP population.

Exploratory Analysis of the Primary Efficacy Endpoint

The odds ratio for the primary efficacy endpoint and its associated two-sided 95% CI will be estimated from a logistic regression model with primary TT and country as fixed factors and composite AROM value at baseline as covariate. Further details will be provided in the SAP.

- subject compliance with the GSC: percentage of days over study period when GSC therapy was performed (as determined from the subject diary)
- global assessment of benefits, evaluated by both the investigator and the subject (or caregiver): at the end of each cycle
- in subjects with an injection planned at Week 16 or 20 of each cycle satisfaction with longer interval collected at the corresponding reinjection visit or the last cycle visit.
- quality of life changes, measured on the EQ-5D 5L and SF-12 scales: change from baseline to Final Visit.

Analysis of the Secondary Efficacy Endpoints

The secondary efficacy endpoints will be summarised descriptively at each relevant visit using the safety/ITT population. Unless otherwise specified, missing values will not be imputed.

Additionally, adjusted mean change from baseline in AROM variables at each relevant postbaseline timepoint and associated two-sided 95% CIs will be estimated from an analysis of covariance (ANCOVA) model with primary TT and country as fixed effects and the appropriate baseline AROM value as covariate. Active UL and LL functions and quality of life questionnaires will be summarised in a similar way as AROM variables.

Percentage of responder subjects at Week 6 after the first injection, according to composite AROM in the primary TT limb, will be analysed in a similar way as for the primary efficacy endpoint.

Using the total number of study days and the total number of days when GSC therapy was not performed (as recorded in the eCRF from the subject diary), the number of days when GSC was performed will be calculated. This percentage of days over the study period when GSC therapy was performed will be calculated by subject and summarized descriptively as a categorical ordinal variable.

